## 1.2. Study Design

This is a multi-center, prospective intra-patient comparator study of urinary radioactivity SUV following both piflufolastat (18F) and flotufolastat (18F) PET in patients with low PSA ( $\leq 0.5$  ng/mL) biochemical recurrence (BCR) of prostate cancer following radical prostatectomy (RP). Approximately 60 patients will be screened for inclusion into the study to obtain a minimum of 52 evaluable patients (i.e. have evaluable PET scans for both piflufolastat (18F) and flotufolastat (18F) available for analysis). As part of their routine clinical care, each patient will be administered a single dose of piflufolastat (18F) on Day 1, followed by a PET scan per standard institutional practice and in line with the PYLARIFY United States Prescribing Information (USPI) (PYLARIFY® [piflufolastat F 18] injection USPI, 2021.). At least 24 hours after the piflufolastat (18F) scan, but within 10 calendar days, all patients will be administered a single dose of flotufolastat (18F) followed by a PET scan. Each patient will receive both radiopharmaceuticals and, thus, serve as their own control.

For the primary endpoint analysis, volumes of interest (VOIs) will be placed over the urinary bladder and radioactivity (SUV metrics) will be assessed following administration of each radiopharmaceutical.

For secondary and tertiary endpoints, both the piflufolastat (18F) and flotufolastat (18F) PET scans will be read by two independent nuclear medicine physicians or nuclear radiologists who are blinded to the patient's clinical history but have been trained to read scans for each respective radiopharmaceutical using product-specific training and in line with the respective FDA-approved USPI for the respective radiopharmaceutical. To facilitate use of the appropriate product-specific training, the independent

readers will be unblinded to the administered agent. Any image interpretation disagreements will be resolved by a third independent adjudicator. Full details are in the Study Image Review Charter.

### 1.2.1. Blinding

The local sites, including the investigator, will not be blinded as each patient will receive piflufolastat (18F) first as part of their routine clinical care (Day 1), followed at least 24 hours later, but within 10 calendar days, by flutufolastat (18F). For imaging interpretation, central readers will be blinded to the radiopharmaceutical and all other clinical data.

### 1.2.2. Primary Analysis

The primary analysis will take place after the last patient has had their last visit, all blinded independent evaluation of the images has been performed and the data is finalized, and clinical DBL has been performed.

## 2. General Considerations

### 2.1. Statistical Hypotheses

The null hypothesis ( $H_0$ ) for the primary endpoint is that there is no difference in urinary bladder  $SUV_{mean}$  between piflufolastat (18F) and flutufolastat (18F), while the alternative hypothesis ( $H_1$ ) is that a difference in urinary bladder  $SUV_{mean}$  does exist.

$$H_0: \text{Difference in urinary bladder } SUV_{mean} = 0$$

$$H_1: \text{Difference in urinary bladder } SUV_{mean} \neq 0$$

### 2.2. Multiplicity Adjustment

No multiplicity adjustments will be made for this study.

### 2.3. Impact of Intercurrent Events

Intercurrent events in this study are defined as any event occurring after administration of piflufolastat (18F) that could potentially interfere with the assessment of the primary and secondary endpoints. These events include but are not limited to the following.

#### 2.3.1. Major Protocol Deviations Affecting Evaluation of PET Scans

Major protocol deviations (PDs) that could potentially affect the evaluation of either the piflufolastat or flutufolastat PET scan will be considered as intercurrent events. These events will be assigned during protocol deviation review, and finalized prior to DBL.

The following adjustments will be made in the primary analysis:

- No adjustment. All data (where applicable) will be included irrespective of the occurrence of the intercurrent event.

The following adjustments will be made as a sensitivity analysis:

- Sensitivity Analysis 1: Patients with this intercurrent event will be excluded from the analysis.

### **2.3.2. Patient Withdrawal After Piflufolastat**

In the unlikely event that patients withdraw from the study after the piflufolastat PET scan but before flutufolastat scan, and therefore would have missing data for the flutufolastat scan, the patient withdrawal will be considered as an intercurrent event.

The following adjustments will be made in the primary analysis:

- Patients with only the piflufolastat PET scan will be excluded.

The following adjustments will be made as sensitivity analyses:

- Sensitivity Analysis 2: We will assume the data from the missing flutufolastat PET scan is the same as the piflufolastat PET scan.
- Sensitivity Analysis 3: We will assume the data from the missing flutufolastat PET scan is missing at random (MAR). A mixed model will be used and will include all available patient data.

## **2.4. Handling of Missing Data**

### **2.4.1. Imputation of Partial Dates for Adverse Events and Concomitant Medications**

No imputation of the start and end dates will be performed.

### **2.4.2. Attributable and Concomitant for Adverse Events and Medications**

The following rules will be used to assign attributable to piflufolastat or flutufolastat for adverse events (AEs) and concomitant to piflufolastat or flutufolastat for medications in relation to partial start dates:

- If completely missing or if year is missing, then assume attributable/concomitant to both piflufolastat and flutufolastat.
- If year is present and month and day are missing, then:
  - If year is the same as administration of piflufolastat, then assume attributable and concomitant to piflufolastat.
  - If year is the same as administration of flutufolastat, then assume attributable and concomitant to flutufolastat.
- If year and month are present and day is missing, then:
  - If year and month are the same as administration of piflufolastat, then assume attributable and concomitant to piflufolastat.
  - If year and month are the same as administration of flutufolastat, then assume attributable and concomitant to flutufolastat.

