10.3 Visit 3 – Scan 2 (Days 2 to 10)

Note: this visit should occur at least 24 hours later than, but within 10 calendar days of Scan 1.

1. Record any changes to concomitant medications and any AEs since Visit 2 (Day 1).
2. Record pre-flotufolastat (^{18}F) administration weight.
3. Administer flotufolastat (^{18}F) and perform PET scan. Results of the image interpretation by the local site reader should be recorded in the eCRF.
4. Schedule patient for a telephone call (Visit 4) on the day after the scan.

10.4 Visit 4 – 24 Hours After Scan 2 (Days 3 to 11; Telephone)

1. Perform post-flotufolastat (^{18}F) scan safety monitoring telephone call, including recording any AEs and changes to concomitant medications since Visit 3.

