#### 2.8. Prior and Concomitant Medications

Medications will be classified as being prior, concomitant to piflufolastat (18F), and/or concomitant to flutufolastat (18F) and are defined as:

- Prior medications are defined as medications with a start date prior to the administration of piflufolastat (18F).
- Concomitant to piflufolastat (18F) medications are defined as medications that are ongoing at the administration of piflufolastat (18F) or have a start date after the administration of piflufolastat (18F).
- Concomitant to flutufolastat (18F) medications are defined as medications that are ongoing at the administration of flutufolastat (18F) or have a start date after the administration of flutufolastat (18F).

Medications may be included in multiple classifications.

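### The partial-start-date rule in SAP 2.4.2 ignores recorded stop dates, so an adverse event that ended before flotufolastat was injected can still be attributed to flotufolastat

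*SAP*

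**What the plan says.** SAP 2.4.2 assigns adverse events as attributable, and drugs as "concomitant to piflufolastat or flutufolastat for medications in relation to partial start dates". It has three branches:

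- Start date or year missing: "If completely missing or if year is missing, then assume attributable/concomitant to both piflufolastat and flutufolastat".
- Only the year known: "If year is the same as administration of piflufolastat, then assume attributable and concomitant to piflufolastat", with a matching line for flotufolastat.
- Year and month known: "If year and month are the same as administration of piflufolastat, then assume attributable and concomitant to piflufolastat", and "If year and month are the same as administration of flutufolastat, then assume attributable and concomitant to flutufolastat".

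No branch mentions the stop date. SAP 2.4.1 adds that "No imputation of the start and end dates will be performed", so no other step brings the end date in.

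Four other places define the categories that 2.4.2 fills:

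- SAP 7.2: a TEAE must have begun or got worse after piflufolastat. Table 3 there places events by when they occur relative to each injection.
- Protocol Table 2: an event between consent and piflufolastat is non-treatment-emergent.
- SAP 2.8, concomitant: the drug must be ongoing at the administration or begin after it.
- SAP 2.8, prior: the start date must precede piflufolastat.

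Stop information is collected. Protocol 12.1 records start and stop dates and times for adverse events. Protocol 9.1.1 captures the dates of each medication, which I take to include the stop.

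**The concern.** A worst-case default is sensible when timing is unknown. Here part of the timing may be known: an event recorded as over before an injection cannot have followed it, whatever its start day. The rule sets that information aside.

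The safety endpoint is the incidence of TEAEs after each scan, so attribution to a tracer is what gets reported. The study is small. If the safety set holds between 52 and 60 patients (an assumption taken from the planned evaluable and screened numbers), one patient wrongly counted moves a tracer's incidence by 1/60 = 1.7 to 1/52 = 1.9 percentage points. The medication summaries by tracer carry the same fault.

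**Working it through.** The documents give no figure for this rule, so the check has two parts: apply 2.4.2 literally to constructed records, then ask how often both tracers share a month or year.

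**Constructed records.** Piflufolastat 14 Nov 2024 and flotufolastat 20 Nov 2024 (illustrative dates inside the Day 2 to 10 window).

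| Record | Start | Stop | SAP 2.4.2 gives | Other text implies |
|---|---|---|---|---|
| A: event | Nov 2024, day unknown | 16 Nov | both tracers | not flotufolastat (ended four days before it) |
| B: event | Nov 2024, day unknown | 12 Nov | both tracers | not treatment-emergent (SAP 7.2, Protocol Table 2) |
| C: drug | unknown | 2022 | both tracers | not concomitant (SAP 2.8) |
| D: drug | 2024 only | Mar 2024 | both tracers | not concomitant (SAP 2.8) |
| E: drug | 2019 only | ongoing | neither tracer | concomitant to both (SAP 2.8) |

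Record A is the clear fault. Whether it began before or after piflufolastat is unknown, so leaving it with piflufolastat is a fair worst case. Attributing it to flotufolastat contradicts its own stop date.

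If the injections straddle a month end (28 Nov and 4 Dec), an event with start December, day unknown, goes to flotufolastat alone, even if it stopped on 2 Dec.

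**How often both tracers share the month.** Visit 3 is on Days 2 to 10, a gap g of 1 to 9 days. Over a 365-day year with Scan 1 dates uniform, the last g days of each of the 12 months push Scan 2 into the next month:

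share in same month = (365 − 12g)/365

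- g = 1: 353/365 = 96.7%
- g = 5: 305/365 = 83.6%, which is also the average over gaps 1 to 9 if these are uniform
- g = 9: 257/365 = 70.4%
- g = 10, if the limit of 10 calendar days is read as a 10-day gap: 245/365 = 67.1%

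share in same year = (365 − g)/365

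- g = 1: 364/365 = 99.7%
- g = 9: 356/365 = 97.5%

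These are shares of scan-date pairs, not of records. They apply to a record only when the known part of its start matches the month or year of the scans. A start date with the year missing goes to both tracers in every case.

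**With a stop-date step added.** Record A moves from both tracers to piflufolastat only. Records B, C and D move from both to neither.

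**The case against.** The strongest reply is that 2.4.2 is not meant to stand alone. SAP 7.2 defines a TEAE before dividing TEAEs by tracer, so record B should never reach the attribution step. SAP 2.8 requires a concomitant drug to be ongoing or to start later, so records C and D fail at the definition. Record E supports this: read alone, 2.4.2 gives a long-standing ongoing drug to neither tracer, which cannot be intended. This reply largely stands. B, C and D are unreconciled passages rather than certain errors. But 2.4.2 has no cross-reference to those sections and the SAP does not say which prevails, so two programmers could differ. A drug such as C, with no start date, also cannot literally meet the definition of prior.

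Record A is not answered this way. Table 3 of the SAP shows the intended result, but 2.4.2 is the rule that places an event when its start is partial, and it places A under flotufolastat.

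It is also fair that over-attribution leans against the sponsor's own product, in keeping with SAP 2.4.4 (missing causality taken as related, missing severity as Grade 3), and that the event listings in SAP 2.12 allow case-by-case review. Neither corrects the summary tables.

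A reader might infer more than the documents support:

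- That every record with a missing month goes to both tracers. It does so only if its year is the year of both administrations.
- That all records stopped before an assigned tracer are misclassified, as a measured error rate. That merely restates how those records were selected.
- That partial event or drug dates are known to occur here. The SAP 2.0 change for partial dates concerns time since diagnosis, prostatectomy and recurrence only.
- That stopped diuretics would be judged prohibited use. Nothing feeds the 2.4.2 flag into the deviation review or the Per Protocol Set.
- That the recording visit could be used at once. Protocol 10.2 and 10.3 list the review of events and drugs before each injection, but no document shows that the visit is stored with each record.

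**Conclusion.** The point holds as a minor fault in a stated rule. A TEAE with an unknown start day in the scan month, and a recorded stop between the two injections, is attributed to flotufolastat whenever both fall in that month: about 70% to 97% of scan-date pairs for gaps of 9 down to 1 day, assuming uniform dates. For records that stopped before piflufolastat, the literal rule conflicts with SAP 7.2 and Protocol Table 2 (events) and with SAP 2.8 (drugs), and precedence is not stated. The number of affected records cannot be derived from the documents and may be small. The effect is confined to event attribution and medication summaries; the primary SUVmean analysis is untouched.

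**What to change.** Before database lock, amend SAP 2.4.2 as follows:

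1. Add a first step: a recorded stop before administration of a tracer excludes attribution or concomitance to that tracer. For a partial stop date, apply this only when its latest possible value is before the administration. Use the recording visit in the same way only if the eCRF stores it.
2. State that the definitions in 7.2 and 2.8 apply first. An event that ended before piflufolastat is then non-treatment-emergent, and a drug stopped before piflufolastat is prior even if its start is unknown.
3. Keep the existing worst-case rule for records that remain undetermined.

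The cost is a few lines of SAP text and derivation code, with no new data for the stop-date step. The small downside is that it depends on stop dates being complete; where they are not, the current rule remains the fallback.

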### **2.4.3. Imputation of Partial Dates for Time Since an Event**

For time since an event (see [Section 2.7](#)) the following rules will be followed for imputing partial dates:

1. Dates with missing month will have the month imputed to January
2. Dates with missing day will have the day imputed to the first of the month

#### 2.4.4. Causality and Severity

For AEs, if causality is missing then the AE will be assumed to be related. If the severity is missing, the AE will be assumed to be Grade 3.

#### 2.5. Baseline

Baseline for a given variable will be defined as the last non-missing measurement prior to the administration of piflufolastat (18F).

#### 2.6. Study Day

For all summaries, study day is defined in respect to the administration of piflufolastat (18F). For visits or events that occur on or after the administration of piflufolastat (18F), study day is defined as:

$$\text{Date of visit or event} - \text{Date of piflufolastat (18F) administration} + 1$$

For visits or events that occur prior to the administration of piflufolastat (18F), study day is defined as:

$$\text{Date of visit or event} - \text{Date of piflufolastat (18F) administration}$$

#### 2.7. Time Since Event

Time since an event in months will be defined as:

$$(\text{Date of event} - \text{date of informed consent} + 1) \times (12/365.25)$$

Events include:

- Initial diagnosis
- Radical prostatectomy
- Biochemical recurrence

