6.2 Inclusion Criteria

1. Male ≥ 18 years of age at Visit 1 (Screening).
2. Documented history of localized adenocarcinoma of the prostate with prior curative intent treatment with RP, experiencing BCR of prostate cancer.
 - a. At least 6 months must have elapsed after RP.
3. Low PSA BCR defined as PSA ≤ 0.5 ng/mL.
4. Scheduled by their treating physician to receive a PSMA (^{18}F) PET scan.
5. Written informed consent obtained from the patient and ability for the patient to comply with the requirements of the study.

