## Version History

This Statistical Analysis Plan (SAP) for Study BED-PSMA-411 is based on the protocol version 4 dated 22APR2024.

SAP Version	Date	Change	Rationale
1.0	09OCT2024	Not applicable	Original version
2.0	24JUL2025	
 
Text for blinding updated to align with imaging review charter to specify that central readers will be blinded to each radiopharmaceutical
 
Additional PSA group added
 
Added detail in Section 6.3.1.1 that for quantitative analyses of paired organs the left and right values would be averaged and summarised.
 
Major deviations that were agreed during PD review to have potentially affected the evaluation of the PET scan(s) will also be summarised
 
Efficacy detection rate tables/figures repeated also for efficacy analysis set
 
Imputation added for time since event variables (see Section 2.4.3)
 
Detection rate summary by the local site reader in Section 8.2 and demographics and baseline table in Section 12.2 will be repeated for the efficacy analysis set.
 
	
 
Updated to align with imaging review charter
 
Additional analysis
 
Clarification
 
Clarification
 
Additional analysis
 
Update due to partial dates
 
Additional analysis
 

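### SAP 2.7 subtracts the dates in the wrong order, so months since diagnosis, prostatectomy and recurrence come out negative

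*SAP*

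**What the plan says.** SAP 2.7 opens with "Time since an event in months will be defined as" and then gives the day count as "Date of event} - \text{date of informed consent} + 1", scaled by 12/365.25. It lists three events: initial diagnosis, radical prostatectomy and biochemical recurrence. SAP 12.6 (prior therapies) and SAP 12.7 (cancer history) summarise the results for the Full Analysis Set, labelled as months since each event.

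Protocol 6.2 fixes the order of events. A patient needs a "Documented history of localized adenocarcinoma of the prostate with prior curative intent treatment with RP, experiencing BCR of prostate cancer", and for the surgery "At least 6 months must have elapsed after RP". He must also be "Scheduled by their treating physician to receive a PSMA (^{18}F) PET scan", which implies that the recurrence was known before he entered.

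SAP 2.4.3 covers incomplete dates for the same variable: "Dates with missing month will have the month imputed to January" and "Dates with missing day will have the day imputed to the first of the month". SAP version 2.0 added this rule with the stated reason "Update due to partial dates".

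**The concern.** A variable that measures time since a past event should be positive: later date minus earlier date. SAP 2.7 puts the earlier date first. Two neighbouring sections suggest a slip. SAP 2.9 derives age with the later year first. SAP 2.6 adds 1 to the study day only on or after the reference date and leaves it out before, which is the case that arises here.

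What is at stake is small but definite. SAP 1 says that its analyses supersede those in the protocol and that departures from it are to be documented in the study report. A programmer who follows 2.7 produces tables of negative months. One who silently corrects it departs from the signed plan.

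**Working it through.** The documents give no worked value for this variable, so there is no figure to reproduce. The check applies the stated rule to example dates.

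**Formulas.** Let d be the number of days from event to consent (positive for a past event). One day is 12/365.25 = 0.03285 month.

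- SAP 2.7 as written: (-d + 1) x 12/365.25
- Operands swapped, inclusive count: (d + 1) x 12/365.25
- Operands swapped, plain elapsed time: d x 12/365.25

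**Worked example.** Surgery on 1 June 2021 and consent on 15 October 2024 (assumed dates) give d = 1,232.

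- As written: (-1,232 + 1) x 12/365.25 = -40.44
- Inclusive: (1,232 + 1) x 12/365.25 = +40.51
- Plain: 1,232 x 12/365.25 = +40.48

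**Other intervals (months).**

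| Days before consent | SAP 2.7 as written | Swapped, with +1 | Swapped, no +1 |
|---|---|---|---|
| 0 | +0.03 | 0.03 | 0.00 |
| 1 | 0.00 | 0.07 | 0.03 |
| 2 | -0.03 | 0.10 | 0.07 |
| 30 | -0.95 | 1.02 | 0.99 |
| 183 (about the 6-month minimum after surgery) | -5.98 | 6.05 | 6.01 |
| 731 | -23.98 | 24.05 | 24.02 |
| 1,827 | -59.99 | 60.06 | 60.02 |

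**Sign.** The rule is negative whenever d is 2 or more. An eligible prostatectomy, and the diagnosis before it, lie about 6 months or more in the past, so they are always negative. Recurrence is negative unless it is dated on the consent day (+0.03) or the day before (0).

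**Size after dropping the sign.** The magnitude as written is d - 1 days and the inclusive count is d + 1 days. The gap is 2 days: 2 x 12/365.25 = 0.07 month. Against plain elapsed time the gap is 1 day, 0.03 month.

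**Imputation rule in SAP 2.4.3, once the sign is right.** The imputed date is never later than the true one, so an interval can only stay the same or lengthen. The figures below assume event dates uniform over a calendar year.

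- Day missing: mean 14.7 days (0.48 month), maximum 30 days (0.99 month).
- Month missing, day known: mean 167 days (5.5 months).
- Month and day missing: mean 182 days (6.0 months), maximum 364 or 365 days (about 12 months).

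Dates in the consent year leave less room. With consent on 15 October 2024, a year-only 2024 prostatectomy must fall by about 15 April to meet the 6-month criterion. The lengthening is then at most 105 days (105 x 12/365.25 = 3.4 months).

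The documents do not say how many dates are partial. If 10% were year-only, a table mean would move by 0.10 x 182 x 0.03285 = 0.6 month; if 25%, by 1.5 months.

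The rule can also disturb the order of events. Take consent on 15 November 2024, surgery on 10 March 2024 and a recurrence recorded only as 2024. The recurrence is set to 1 January 2024, which is 10.5 months before consent against 8.2 for the surgery.

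**The case against.** The strongest reply is that this is harmless. The intent is plain from the variable's name and the table labels, a column of negative months would be noticed at the first table review, and nothing inferential uses the variable. All of that is true, and it limits the weight of the point. It does not make the rule right: 2.7 is an operative derivation, no sign convention rescues it, and reading it as a signed offset from consent fails too, because the added 1 then misplaces every past date by a day.

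A reader might infer three stronger things that the documents do not support.

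- That the earliest-date rule in 2.4.3 is a second error. It is a pre-specified convention that contradicts nothing else in the plan. Midpoint imputation is a different preference. The lengthening is real but can be zero (a true date of 1 January, or the first of a month), and its extent is unknown without the count of partial dates.
- That the tables serve to demonstrate the 6-month interval after surgery. Nothing in the SAP gives them that role. Eligibility is reviewed at Visit 1 (Protocol 10.1), a breach is a protocol violation (Protocol 14), and no analysis set is defined by this variable (SAP 3 and 12.3.1).
- That every value has the wrong sign. A recurrence dated on the consent day or the day before is an exception, though a minor one.

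**Conclusion.** The operand order in SAP 2.7 is wrong as written. It gives negative months for every eligible prostatectomy and the diagnosis before it, and zero or negative months for a recurrence dated before the consent day. Removing the minus sign leaves the value 2 days (0.07 month) short of the inclusive count.

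This rests on the entry criteria for the order of events and on the absence of any absolute value or sign convention in the SAP. It does not depend on the example dates.

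The consequence is confined to the descriptive summaries in SAP 12.6 and 12.7. The primary test, detection rates, safety analyses and sample size do not use the variable. This is a minor correction that costs nothing to make. The imputation rule supports an optional note only.

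**What to change.** Replace the definition in SAP 2.7 with (date of informed consent - date of event + 1) x 12/365.25. If plain elapsed time is intended, leave out the + 1. State which is meant. This changes one line of SAP text and one line of code.

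Optional: keep the rule in 2.4.3, report with the tables how many dates were imputed for each event, and run a check that diagnosis <= prostatectomy <= recurrence <= consent after imputation. The count and the check need a little programming. If imputed dates were to be moved to respect that order, the SAP would also need a rule for which date gives way when several are partial, so a check that flags cases is the cheaper choice.
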